In year 2, We will recruit adult patients (aged 40-70; n=54) of the UPMC General Internal Medicine-Oakland (GIMO) practice not meeting the US aerobic activity goal of 150 minutes/ week of at least moderate intensity physical activity who can safely increase physical activity without supervision and have who also have at least one of the following common cardiometabolic risk factors for which improving physical activity levels can be beneficial (high blood pressure: > 129 mm hg SBP or > 89 mm hg DBP or medication use, high fasting glucose: > 100 mg/dl or high HbA1c: ≥ 42 mmols/mol or medication use, overweight/ obesity: BMI ≥ 25 kg/m²). As low physical activity levels have been associated with numerous poor cardiometabolic health outcomes, the primary intervention goal will be achievement of the US physical activity goal. Intervention materials will be developed using a patient/provider centered approach and delivered weekly over 3 months via the existing GOALS online platform with participants self-tracking behavior (using a commercial wrist worn activity monitor). An additional 9 months of "maintenance" support will be provided via the GOALS platform and email/phone contact from a coach. Using an online approach will reduce staff and participant burden and will allow for wider dissemination of the program. A prospective randomized, active control design will be used to determine changes in the primary outcomes of objectively measured step counts, % of individuals meeting the moderate-vigorous physical activity goal. Active

control participants will be given a commercial wrist worn activity monitor and information on the CDC activity recommendations.

4. * What kind of study is this?

Single-site study

5. * Will an external IRB act as the IRB of record for this study?

Yes No

6. * Local principal investigator:

[name]

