a. We hypothesize that participants randomized to ActiveGOALSV2 + PAT will have significantly larger (a) changes in step counts/day and % meeting moderate-vigorous physical activity goal of 150 minutes/week (to 12 months) compared to the active PAT control group. Primary outcomes will include changes in step/day and meeting the activity goal from validated research-grade PATs. Secondary outcomes will include changes in body weight, blood pressure, glycemic control, and cholesterol from study collected clinical outcomes and health questionnaires.

b. EHR data will also be used to assess program success, including program reach (comparing patients enrolling/not enrolling) and examining relationships between changes in EHR-recorded cardiometabolic outcomes and primary PA outcomes from PATs. Finally, pre-enrollment factors will be examined in relation to program success, toward better future identification of patients who may benefit from referral to programs for PA improvement. Results of this aim will be used toward developing a technology enabled referral system to an appropriate lifestyle intervention strategy with program evaluation methods that use EHR data

2. * Describe the relevant prior experience and gaps in current knowledge including preliminary data. Provide for the scientific or scholarly background for, rationale for, and significance of the research based on existing literature and how it will add to existing knowledge:

Advice from clinicians can significantly influence lifestyle behaviors. Following the American College of Sports Medicine, the American Heart Association (AHA) has recently issued a statement endorsing clinical physical activity prescription

programs. [15,18,38] In their statement the AHA outlines advantages of clinical PA advice and referral, including improved patient outcomes and lower healthcare costs.[38] Clinically administered advice on physical activity has also been shown to increase patient satisfaction with clinical care.[6,7] However, the concept of treating low physical activity levels through clinical practice is relatively new and often not part of standard care.[8-11]

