- I bring a novel skill set to this research. The additional training received through this K01 will uniquely position me to lead future efforts leveraging available technologies and clinical resources toward developing feasible programs for physical activity referral. I have an in-depth knowledge of body-worn PATs and a strong foundation in public health research. Through my K12, I acquired knowledge of Patient-Centered Outcomes Research. K01 funding will enable me to receive the training an experience that would enable me to utilize quantitative methods when involving stakeholders, to gain expertise in the use of EHR data in assessing clinically-integrated interventions, and to learn how to best utilize PAT output to

encourage behavior change. Process development strategies and pilot intervention data acquired during the K01 will be essential to being able to move forward in my own unique career trajectory.

Study Design

1. Total number of subjects to be enrolled at this site (enter -1 for chart reviews, banking, registries):

54 to undergo research procedures; 200 to undergo screening

2. Describe and explain the study design:

Fifty-four participants will be randomized to one of two groups: physical activity tracker (PAT)+ActiveGOALSV2 or the active control: PAT only.

3. Describe the primary and secondary study endpoints:

1. Average Step Counts per day
2. % of participants achieving the 150 minute/week aerobic activity goal

Secondary: changes in body weight, waist circumference, blood pressure, glycemic control (fasting blood glucose and hba1c), and cholesterol (ldl, hdl, triglycerides) from study collected clinical outcomes. Quality of life and PROMIS score from health questionnaire.

4. Provide a description of the following study timelines:

Duration of an individual subject's active participation:

12-15 months

Duration anticipated to enroll all subjects:

12 month enrollment period

Estimated date for the investigator to complete this study (complete primary analyses):

12/31/2022

5. List the inclusion criteria:

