*** Identify the subgroups and provide a justification:**

Children are excluded. The physical activity requirements of 150 minutes of physical activity pertain only to adults. The intervention is designed for adults- materials specific to children would have to be designed for children.

8. Describe the power analysis used and cite your method of statistical analysis.

If a power analysis is not possible, thoroughly justify the sample size required for the study, including appropriate literature citation (alternatively provide page reference in attached protocol):

For our Aim 1a primary outcomes, we hypothesize that participants randomized to ActiveGOALSV2 + PAT will have significantly larger (a) increases in step counts/day and % meeting moderate-vigorous physical activity goal of 150 minutes/week (to 12 months) compared to the active PAT control group. Descriptive analyses and graphic displays will be used to identify outliers, missing data, and pattern of attrition. To ensure rigor, the primary analytic strategy will be a linear or generalized mixed-effect models approach in which treatment group, time, and time by group interaction are treated as fixed effects, and subject is treated as a random effect to account for individual subject variability (two sided hypothesis test; .05 level). Mixed models are applicable to longitudinal datasets that contain missing observations, (assuming data is missing at random). Regression modeling will be conducted to adjust for important covariates. We will perform similar analyses to examine changes in secondary outcomes. Descriptive statistics on patient experience, beliefs/attitudes related to maintenance of physical activity changes, and program cost will also be reported.

Power and sample size: For a 2 sided test with alpha level set at .05, and assuming 20% attrition at 12 months, we plan to recruit 54 participants to identify clinically relevant mean difference between randomized groups at 12-months of 2000 steps/day (with a power of .80), and 35% meeting MVPA goal (with a power of .80), given reference mean (sd) values were calculated from baseline waist worn accelerometer data from the current K12 of: 5250 (2200) steps/ day and we assume 5% meeting goal at baseline in the control group.

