Coverpage

Title: Advancement of Clinical Referral to Physical Activity for Cardiometabolic Disease Prevention

Brief Title: The Clinical Referral to Activity Study

NCT: NCT04743856

Date Created/Modified: November 3, 2025

Statistical Analyses

6.1.6 Statistical Analyses: For our primary outcomes, we hypothesize that participants randomized to ActiveGOALSV2 + PAT will have significantly larger (a) increases in step counts/day and % meeting MVPA goal of 150 minutes/week (to 12 months) compared to the active PAT control group. Descriptive analyses and graphic displays will be used to identify outliers, missing data, and pattern of attrition. To ensure rigor, the primary analytic strategy will be a linear or generalized mixed-effect models approach in which treatment group, time, and time by group interaction are treated as fixed effects, and subject is treated as a random effect to account for individual subject variability (two sided hypothesis test; .05 level). Mixed models are applicable to longitudinal datasets that contain missing observations, (assuming data is missing at random). Regression modeling will be conducted to adjust for important covariates. We will perform similar analyses to examine changes in secondary outcomes. Descriptive statistics on patient experience, beliefs/attitudes related to maintenance of PA changes, and program cost will also be reported. Mixed models are used to help account for missing data and no adjustments will be made for multiple comparisons.

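### The binary primary outcome has no named contrast, effect scale or test; the stated .80 power fits a 12-month comparison, but a logit-scale interaction test would have about .4 to .5

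*SAP*

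**What the plan says.** SAP section 6.1.6, repeated in Protocol, Study Design item 8, calls for a linear or generalized mixed model in which "treatment group, time, and time by group interaction are treated as fixed effects, and subject is treated as a random effect", tested two-sided at .05. No coefficient, link, effect measure or test statistic is named.

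The target is worded differently from place to place:

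- The SAP hypothesis is "significantly larger (a) increases in step counts/day and % meeting MVPA goal of 150 minutes/week (to 12 months"), and Protocol, Study Aims item 1a says "Primary outcomes will include changes in step/day and meeting the activity goal from validated research-grade PATs". Both describe a change.
- Protocol, Study Design item 3 lists the percentage "of participants achieving the 150 minute/week aerobic activity goal". This is the measured quantity, with no contrast attached.
- The power paragraph in Study Design item 8 refers to a "clinically relevant mean difference between randomized groups at 12-months of 2000 steps/day" and, for the goal outcome, to "35% meeting MVPA goal (with a power of .80"). It adds that "we assume 5% meeting goal at baseline in the control group". It gives no control rate at 12 months and no rate for the active arm at baseline.

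Visits are at baseline, 6 and 12 months. The plan is for 54 participants with 20% attrition at 12 months. The SAP makes no adjustment for multiple comparisons.

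**The concern.** A hypothesis about increases, set beside a model with a group-by-time term, is often tested through that interaction. In a logistic model the interaction compares changes in log odds, so it leans on the baseline rate as much as on the 12-month rate. At 5% baseline there is almost nothing to estimate that rate from. The power paragraph appears to describe a different quantity, the difference between arms at 12 months.

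Two analysts could therefore follow the same text and run tests with very different chances of detecting the planned effect on one of two primary outcomes. The choice could also be made after seeing the data. With three visits the interaction itself has more than one form: a 12-month term, a joint test over visits, or a linear slope. Steps share the unnamed contrast, with less at stake.

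**Working it through.** **1. The plan's own figure.** Inputs from Study Design item 8: 54 recruited, 20% attrition, two-sided .05, 5% control rate, 35%. Assumed: 1:1 allocation, and control still at 5% at 12 months. Analysed per arm: 27 × 0.8 = 21.6. Pooled two-proportion power is Φ{[d√n − 1.96√(2p̄q̄)] / √(p₁q₁ + p₂q₂)}.

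- 35% as a difference (5% vs 40%): d = .35, p̄ = .225. (1.627 − 1.157)/.536 = 0.875, power **.81**.
- 35% as a rate (5% vs 35%): d = .30, p̄ = .20. (1.394 − 1.109)/.524 = 0.545, power **.71**. It reaches .80 only with all 27 per arm and no attrition.

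The difference reading fits better, though not perfectly: solving for .80 gives 22 per arm, or 28 after attrition, hence 56 rather than 54.

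**2. Baseline information.** Expected baseline events per arm: 27 × .05 = 1.35. Chance that at least one arm has none: 1 − (1 − .95²⁷)² = 1 − (1 − .250)² = .44.

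**3. Power of the candidate tests.** Trials were simulated from a random-intercept logistic model fitted by maximum likelihood with Gauss-Hermite quadrature: 27 per arm, three visits, 5% at baseline in both arms, then 5% control and 40% active at 12 months. The active 6-month rate was either 40% or midway at 22.5%. The random-intercept (subject) SD is not in the documents; .5, 1 and 2 were used, with 20% missing completely at random at 12 months only. There were 2000 trials per scenario (Monte Carlo SE about .01).

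| Test | Power |
|---|---|
| 12-month interaction, logit, likelihood ratio | .40–.51 |
| Joint 2-df interaction, likelihood ratio | .34–.49 |
| Linear-time interaction, likelihood ratio | .29–.44 |
| 12-month contrast from the same model, likelihood ratio | .86–.88 |
| Plain 12-month two-proportion test | .84–.86 |
| Change in percentage points, completers' t test | .73–.83 |

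Separately coded runs of 1000 trials, with subject SD from 0 to 3 and some dropout by 6 months, gave .41–.57 for the 12-month interaction and .86–.90 for the 12-month contrast. A further check gave .44–.48 against .85–.88, and, with a 10% baseline rate, .42–.58 against .78–.81.

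**4. If control also rises.** The active control makes this plausible: "control participants will be given a commercial wrist worn activity monitor and information on the CDC activity recommendations". With 15% vs 50% at 12 months, the interaction has .26–.35 and the 12-month contrast .72–.75.

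**5. Type I error at nominal .05 (3000 null trials).** 12-month interaction, likelihood ratio: .069–.087. 12-month contrast, likelihood ratio: .049–.074, or up to .075 with a shared baseline.

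**6. Steps.** Difference 2000 and SD 2200 from item 8; 22 and 21 analysed. The correlation r is not in the documents.

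- Unadjusted 12-month comparison: noncentrality 2000/[2200√(1/22 + 1/21)] = 2.98, power .83.
- 12-month difference adjusted for baseline, SD 2200√(1 − r²): .86, .89, .92 and .95 at r = .3, .4, .5 and .6.
- Change contrast in the planned random-subject model, keeping dropouts' earlier visits: SE² = 2·2200²·[(1 − r)/(1 + r)]·[(1 + 2r)/21.5 + 1/27]. SE = 762, 708, 648 and 581. Φ(2000/SE − 1.96) = .75, .81, .87 and .93. A t reference lowers these by one or two points.

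**The case against.** The strongest reply is that the low figure belongs to a reading the documents do not choose. The power paragraph speaks of groups at 12 months, and the hypothesis is worded in percentages, which suggests a percentage scale. On either of those readings power is near or above .80 while control stays at 5%. With arms equal at baseline by randomisation, a larger percentage-point change and a 12-month difference also target the same effect, so the differing descriptions are less of a conflict than they look.

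All of that stands. A reader might infer that the plan tests the logit interaction, or that the trial is underpowered for its goal outcome. The documents support neither inference. What remains open is the scale and the test, and nothing in the SAP carries the 12-month framing of the power paragraph into the analysis.

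The simulated figures do rest on inputs that the documents do not supply. Varying the subject SD and the baseline rate moved interaction power only between about .4 and .58, and the gap to the 12-month contrast persisted. The interaction test also rejects too often under the null, so correcting for size would lower its power further.

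For steps, the objection largely succeeds: under the planned model a change contrast falls below .80 only if the correlation is under about .4.

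**Conclusion.** The gap is real and should be fixed. The SAP gives a model and a verbal hypothesis but does not say which contrast, on which scale, by which test, decides the binary primary outcome. The stated .80 fits a 12-month between-group comparison of 5% vs 40%. A common alternative reading of the same text, the 12-month interaction on the logit scale, has likelihood-ratio power of about .4 to .5 (up to about .57 under other subject SDs or a 10% baseline rate), against about .85 to .9 for the 12-month contrast from that model.

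These figures assume 1:1 allocation, 5% at baseline in both arms, control staying at 5%, and a subject SD chosen by assumption. The conclusion is conditional on the choice of test; it does not show that the sample size is inadequate. That 35% means a difference is the better-fitting reading, not a proven one.

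**What to change.** In SAP section 6.1.6:

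- **Goal outcome.** Name the 12-month between-group contrast from the planned logistic mixed model, with visits as categories, as the primary test, by likelihood ratio. Report the model-standardised 12-month risk difference with its 95% CI. Keep the group-by-time interaction as supportive.
- **Steps.** Name the 12-month difference adjusted for baseline as the primary contrast.

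In Protocol, Study Design item 8: state that 35% is a difference (5% vs 40%) if that is what was meant, state the assumed control rate at 12 months, and restate power for the named test.

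The cost is wording; no new data are needed. The likelihood-ratio test can run slightly above its nominal level at this size (about .05 to .075), and the SAP should say so. The documents do not say whether outcome data have been seen: the protocol's estimated completion is 12/31/2022 and the SAP cover is dated November 3, 2025. If they have been seen, the change must be reported as post hoc, with the interaction result beside it.
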